### **Reporting to Pharmaceutical Companies providing Study Drug**

All SAEs, whether related or not related to study drug, and pregnancies must be reported to BMS within 24 hours. SAEs must be recorded on BMS or an approved form; pregnancies on a Pregnancy Surveillance Form.

**SAE Email Address:** [REDACTED]

**SAE Facsimile Number:** [REDACTED]

- An SAE report should be completed for any event where doubt exists regarding its seriousness.
- For studies with long-term follow-up periods in which safety data are being reported, include the timing of SAE collection in the protocol.
- If the investigator believes that an SAE is not related to study drug, but is potentially related to the conditions of the study (such as withdrawal of previous therapy or a complication of a study procedure), the relationship should be specified in the narrative section of the SAE Report Form.

- If only limited information is initially available, follow-up reports are required. (Note: Follow-up SAE reports should include the same investigator term(s) initially reported.)

If an ongoing SAE changes in its intensity or relationship to study drug or if new information becomes available, a follow-up SAE report should be sent within 24 hours to BMS using the same procedure used for transmitting the initial SAE report. All SAEs should be followed to resolution or stabilization. All SAEs should be followed to resolution or stabilizationIf only limited information is initially available, follow-up reports are required. (Note: Follow-up SAE reports should include the same investigator term(s) initially reported.)

If an ongoing SAE changes in its intensity or relationship to study drug or if new information becomes available, a follow-up SAE report should be sent within 24 hours to the BMS (or designee) using the same procedure used for transmitting the initial SAE report.

All SAEs should be followed to resolution or stabilization.

The Sponsor/Investigator will ensure that all SAEs in the clinical database are reported to BMS and any applicable health authority during the conduct of the study including periodic reconciliation.

## 8 Statistical Considerations and Evaluation of Results

### 8.1 Study Endpoints

#### 8.1.1 Primary Endpoint:

The primary objective of this study is to establish the feasibility of completing a combined chemoradiation-nivolumab regimen followed by adjuvant nivolumab. Feasibility of completing adjuvant phase therapy is a key relevant clinical question in ongoing NPC research, as the efficacy of the current standard of care of platinum-based concurrent and adjuvant phase chemotherapy is in question but its toxic effects are severe, resulting in frequent early discontinuation of adjuvant therapy. Adjuvant nivolumab is likely to be much more tolerable and feasible and if feasibility of the program is established, this will open the possibility of testing its efficacy in various subsets of patients.

**Feasibility of treatment completion:** The primary endpoint of the study will be the rate of completion of all adjuvant immunotherapy, in comparison to the rate of completion of a standard adjuvant cisplatin-based platform. The rate of completion of all adjuvant therapy by patients treated at the MTD schedule will be determined and compared to a historical control rate of 52%.

#### 8.1.2 Secondary Endpoints

**Efficacy:** ORR as assessed by the study investigator by RECIST 1.1 criteria. The ORR is defined as the best overall response (BOR) recorded from the first day of treatment until time of assessment.

**Safety and tolerability:** Evaluate the number and frequency of Adverse Events (AEs) as determined by National Cancer Institute Common Toxicity Criteria (NCI-CTC) version 4.0 by investigator assessment.

- To determine the clinical response as judged by the investigator;
- To determine the overall response rate from the first day of treatment to 1 year post-treatment, as determined by RECIST 1.1 criteria;
- To determine the locoregional control rate at 1 year post-treatment;
- To determine the distant metastasis rate at 1 year post-treatment;
- ;
- To determine the rate of EBV DNA clearance at end of chemoradiation and at 1 year post-treatment;  
To determine the acute and late toxicity rates according to CTCAE v5.0, including immune-related adverse events (AEs);
- To assess patients' quality of life from baseline through 1 year post-treatment;

### 8.1.3 Correlative Studies

#### Exploratory studies

- To determine the overall survival rate at 5 year post-treatment

When adequate tissue is available, To determine whether PDL1-positive immunohistochemistry and novel quantitative assays correlate to clinical outcome;

- To determine if the density of infiltrating CD3+ T cells/ $\mu$ m^2 correlates to clinical outcome;
- To monitor immune changes by flow cytometry in the circulating T cell response to EBV antigens;
- To compare the change in the circulating T-cell repertoire by TCR sequencing and single-cell T-cell profiling;
- To quantify treatment-induced changes over time in the circulating T cell immune response to EBV using TCR sequencing and enzyme-linked immunospot (ELISPOT) assays.

## 8.2 Determination of Sample Size and Accrual Rate

### 8.2.1 Sample Size and Power Estimate

We expect the true completion rate of this combined chemoradiation-nivolumab regimen followed by adjuvant nivolumab to be 70%, versus the null hypothesis of 50% (the rate of completion of a standard adjuvant cisplatin-based platform is 52%).

Simon's two-stage design will be used to test this endpoint. In the first stage, 22 patients will be accrued. If 11 or fewer completions, the study will be stopped. Otherwise, 18 additional patients will be accrued for a total of 40 participants.. The null hypothesis will be rejected if 26 or more completions are observed in 40 patients. This design yields a type I error rate of 0.05 and power of 80% when the true completion rate is 0.7.

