Study Design	
 
This is a phase II multi-institution, single-arm, open label clinical trial of concurrent and adjuvant nivolumab in Stage II-IVB endemic-type nasopharyngeal carcinoma patients who plan to undergo chemoradiation therapy for treatment of their cancer.
 
A run-in phase will precede expansion, to establish basic feasibility of the nivolumab schedule. The run-in cohorts will include 6 patients at each dose schedule, with 2 planned changes to the dose schedule if >33% toxicity or other dose limiting toxicity (DLT) is observed. A minimum of 6 patients and maximum of 18 patients may be enrolled in the run-in phase.
 
A total maximum of 40 evaluable patients will be enrolled for the primary endpoint. This design yields a type I error rate of 0.05 and power of 80% if the true rate of completion of adjuvant therapy is 0.7.
 
At the starting dose schedule, patients will receive nivolumab for 1 cycle prior to initiation of chemoradiation (approximately 14 days). Patients will subsequently continue with nivolumab every 14 days until completion of chemoradiation. If a dose schedule shows >33% toxicity or other DLT, then subsequently enrolled patients will be treated at the next dose schedule. In dose schedule 2, patients will start nivolumab concurrent with start of chemoradiation. In dose schedule 3, patients will start nivolumab after completion of chemoradiation (adjuvant nivolumab only). All patients will receive the same dose of nivolumab (240mg).
 
DLT criteria are grade <math>\geq</math>3 immune-related adverse events, need to hold nivolumab for >28 days due to toxicity, and for patients receiving concurrent nivolumab with chemoradiation, inability to complete chemoradiation or need to hold chemoradiation for >3 days due to immune-related toxicity.
 
Adjuvant therapy with nivolumab for 6 cycles will start at 4 weeks following completion of chemoradiation, or when immune-related toxicities are at grade 1 or lower, whichever comes later.
 
Patients will be followed for overall response rate, locoregional control and distant metastasis rates, and overall survival rate for 1 year after end of treatment.
 

Number of patients	A maximum of 40 evaluable patients will be enrolled in the study using a Simon's two-stage design for the primary endpoint. Non-evaluable patients will be replaced per the replacement policy.

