The very pressing question of whether there is any oncologic benefit to be accrued from the use of adjuvant chemotherapy in locoregionally advanced NPC was studied in a recent randomized trial from China. This phase III study compared RT with weekly CDDP followed either by 3 cycles of CDDP/5-FU or no adjuvant treatment. In 508 patients, the study found no statistically significant improvement in either progression-free or overall survival from the addition of adjuvant cytotoxic chemotherapy. Of note, in this study, 82% of patients assigned to the arm receiving weekly cisplatin plus adjuvant cisplatin-5FU started adjuvant chemotherapy, but only 63% were able to complete all 3 adjuvant cycles (52% therefore started and completed all adjuvant therapy). During adjuvant chemotherapy, 42% of patients experienced grade 3-4 toxic effects; 49% had dose reductions and 69% experienced delays in treatment. This is notable given that there was no apparent increase in rates of completion or better tolerance compared to results from the earlier era.

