### **2.4 Endpoints**

#### **2.4.1 Primary Endpoints**

- The primary endpoint will be the rate of completion of adjuvant immunotherapy, in comparison to the rate of completion of a standard adjuvant cisplatin-based platform (historical control). This will be determined based on the ability to complete all prescribed concurrent and/or adjuvant nivolumab without discontinuation for disease progression or toxicity.

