### 3.4 Number of Subjects

A maximum of 40 evaluable patients will be enrolled in the study using a Simon's two-stage design for the primary endpoint. Patients who are enrolled at the maximally tolerated dose of

nivolumab during the run-in phase will be included in the determination of the primary endpoint. Non-evaluable patients will be replaced per the replacement policy (see section 8.2.5). For the primary endpoint, this design yields a type I error rate of 0.05 and power of 80% if the true rate of completion of adjuvant therapy is 0.7.

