### **8.2.4 Statistical plan**

Simon's two-stage design will be used to test the primary endpoint for the phase II study. The null hypothesis that the completion rate is 0.5 will be tested against a one-sided alternative 0.7. In the first stage, 15 patients will be accrued (including 6 patients at MTD schedule from the run-in phase). If there are 7 or fewer completions in these 15 patients, the study will be stopped. Otherwise, 13 additional patients will be accrued for a total of 28 patients accrued in the expansion phase. The null hypothesis will be rejected if 18 or more completions are observed in 28 patients. This design yields a type I error rate of 0.09 and power of 80% when the true completion rate is 0.7.

We propose that the final decision about the direction of future strategy and additional expansion studies should be made based on careful analysis of subpopulations with particular attention to feasibility, toxicity, and observed immunodulatory responses.

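### The completion rate is compared with a 52% historical control, but the Simon rule is set against 50% with no reason given; the type I error stated as 0.05 is 0.066 at the named control

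*Combined protocol and SAP*

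**What the plan says.** Section 2.4.1 defines the primary endpoint as the completion rate of adjuvant immunotherapy, "in comparison to the rate of completion of a standard adjuvant cisplatin-based platform (historical control"); the abstract's primary objective does the same. Section 8.1.1 puts a number on that control: the rate in patients treated at the MTD schedule "will be determined and compared to a historical control rate of 52" per cent. Section 8.2.3 repeats this. The figure comes from the randomised adjuvant cisplatin-5FU trial described in section 1.1.2, where 82% started adjuvant therapy and 63% completed it, so that "52% therefore started and completed all adjuvant therapy".

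The test uses a different rate. Section 8.2.1 sets an expected rate of 70% "versus the null hypothesis of 50% (the rate of completion of a standard adjuvant cisplatin-based platform is 52" per cent). Its rule is to stop with 11 or fewer completions in 22 patients and to reject the null with 26 or more in 40. It states type I error 0.05 and power 80% at 0.7. Section 8.2.4 describes another rule: stop with 7 or fewer in 15, reject with 18 or more in 28, type I error 0.09, power 80%. It uses the same null: "The null hypothesis that the completion rate is 0.5 will be tested against a one-sided alternative 0.7".

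Two summaries give the error rate with no null at all. The abstract says "This design yields a type I error rate of 0.05 and power of 80% if the true rate of completion" is 0.7, and section 3.4 says "this design yields a type I error rate of 0.05 and power of 80% if the true rate of completion" is 0.7.

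**The concern.** This is a single-arm trial, so the null rate carries the whole comparison with standard adjuvant chemotherapy. If the null is rejected, the result will be read as better completion than the 52% control. The error rate that matters for that reading is the chance of rejection when the true rate is 52%, and the plan does not give it. Where the endpoint is defined against the historical control and 0.05 is quoted without a null, a reader will naturally take 0.05 as the error against that control. Because the null lies below the control, the discrepancy can only favour a positive result.

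**Working it through.** **Inputs.** Null 0.50, alternative 0.70 and the 22/40 rule: section 8.2.1. The 15/28 rule: section 8.2.4. Control 0.52: sections 8.1.1 and 8.2.3. Unrounded control: 0.82 × 0.63 = 0.5166, from section 1.1.2.

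**Formula.** With n1 patients in stage 1, stopping at r1 or fewer completions, n patients in total and rejection at r or more completions:

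P(reject | p) = Σ over x = r1+1, …, n1 of Bin(x; n1, p) × P[Bin(n − n1, p) ≥ r − x]

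For 22/40 the sum runs over x = 12 to 22, and the second factor is P[Bin(18, p) ≥ 26 − x].

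**Step 1: reproduce the plan's figures.** For 22/40, power at 0.70 is 0.803, matching the stated 80%. The rejection probability at 0.50 is 0.0396, so 0.05 holds as a ceiling but is not the attained value. Lowering the threshold to 25 gives 0.0737 at 0.50, so neither 25 nor 26 yields exactly 0.05. For 15/28, the results are 0.0900 at 0.50 and 0.801 at 0.70, both as stated.

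**Step 2: evaluate the same rules at the named control.**

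| Rule | p = 0.50 | p = 0.5166 | p = 0.52 | p = 0.70 |
|---|---|---|---|---|
| 22/40, reject at 26 or more | 0.0396 | 0.0611 | 0.0664 | 0.8028 |
| 15/28, reject at 18 or more | 0.0900 | 0.1220 | 0.1294 | 0.8009 |

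Excess over the stated error at 0.52:
- 22/40: 0.0664 − 0.05 = 0.0164, or 1.6 percentage points. The ratio to the attained error at 0.50 is 0.0664 / 0.0396, about 1.7.
- 15/28: 0.1294 − 0.09 = 0.0394, or 3.9 percentage points.

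Rounding 51.66% up to 52% does not create the problem: at 0.5166 the 22/40 rule already gives 0.061.

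**Step 3: cross-check.** Ignoring the stage 1 stop, 26 or more of 40 has probability 0.0404 at 0.50 and 0.0676 at 0.52. The two-stage values lie just below these, as they should.

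**Step 4: what 0.05 against 52% would require.**
- Same 22/40 sizes, threshold raised to 27: error 0.034 at 0.52, power 0.702 at 0.70.
- Same first stage, 46 patients in total, threshold 30: error 0.048, power 0.802. No two-stage design with fewer than 46 patients meets both limits.

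**The case against.** The strongest reply is that nothing is miscalculated. The 0.05 belongs to the declared null of 0.50, where it holds, and section 8.2.1 shows 50% and 52% in one sentence, so a reader of the statistical section sees both. That is correct, and the point is not an arithmetic error. It does not help a reader of the abstract or section 3.4, where neither rate appears, and even section 8.2.1 does not give the error at 52%.

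Second, 52% is a rounded estimate from one trial. Section 1.1.2 also cites 50–60% across past trials and 55% in the Intergroup study, so 50% is at the edge of the plan's own range. But the plan does not offer this as its reason, and 50% is the lowest value in that range. At 55% the 22/40 rule rejects with probability 0.130. Uncertainty in the control is a real limitation that moving the null to 52% would not remove.

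Third, the effect is small: 1.6 points, with a rejection threshold of 26/40 = 65%, which is 13 points above the control. This stands, and it limits the weight of the point. So does the observation that 22/40 versus 15/28 is a separate contradiction. The 40-patient maximum in the abstract and sections 3.4, 8.2.5 and 8.2.6 agrees with 22/40, which makes the smaller gap the more likely one to apply.

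**Conclusion.** The concern holds. The comparator named for the primary endpoint is 52%, the decision rule is set against 50%, and no reason is given. The stated 0.05 does not hold at the named control: it is 0.066 under 22/40. Under 15/28, the stated 0.09 is 0.129. Power is 0.80 at 0.70 in both cases. This is a modest misstatement of the error rate for the trial's one formal test, and it should be corrected; it does not invalidate the design. The figures assume that patients complete independently with a common probability, that the stopping and rejection rules are followed exactly at the planned sizes, and that 52% is a fixed, known rate.

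**What to change.** First decide which design governs: 22/40 (section 8.2.1) or 15/28 (sections 8.2.3 and 8.2.4).

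If 22/40 governs, make one of two changes in sections 8.2.1, 8.2.4 and 3.4 and in the abstract:
- (a) state the null as 0.52 with type I error 0.066; or
- (b) keep 0.50, give the reason, and report type I error 0.040 at 0.50 and 0.066 at the 52% control.

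Either costs about one sentence in each place. Power stays 0.80 at 0.70, and no threshold or patient number changes. The only price is a slightly less favourable stated error.

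If 15/28 governs, report 0.090 at 0.50 and 0.129 at 0.52, and replace the 0.05 in section 8.2.1, section 3.4 and the abstract.

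A redesign is needed only if the sponsor wants 0.05 or less against 52%. The cost is then either power of 0.70 (27 or more of 40) or six more patients (30 or more of 46, with power kept at 0.80).

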### 8.2.2 Run-in phase

Six patients will be enrolled for the initial run-in phase, with nivolumab dosing of 240 mg. Enrollment will cease until all 6 patients have completed concurrent chemoradiation and nivolumab. If 3 or more of the first 6 patients experience grade 3-4 immune related toxicity or other DLT during concurrent chemoradiation and nivolumab therapy, then the run-in will restart at dose schedule 2 with 6 additional patients. In dose schedule 2, patients will start nivolumab

concurrent with chemoradiation and will not start nivolumab prior to chemoradiation. If 3 or more of the first 6 patients experience grade 3-4 immune related toxicity or other DLT during concurrent chemoradiation and nivolumab at dose schedule 2, then the dose schedule will be changed to dose schedule 3 and the run-in will restart at dose schedule 3 with 6 additional patients. In dose schedule 3, patients will start nivolumab in the adjuvant phase only and will not receive nivolumab before or during chemoradiation, and the toxicity of nivolumab will be assessed during the adjuvant phase. No dose escalation or reduction will be allowed in the run-in phase. Dose modifications of nivolumab are not permitted from the standard dose of 240 mg every 14 days.

The run-in will cease when 4 or more patients have completed chemoradiation and nivolumab therapy at the same nivolumab dose schedule without experiencing grade 3-4 toxicity or other DLT (this will be considered the maximally tolerated dose), or alternatively, if 3/6 patients have experienced grade 3-4 toxicity at dose schedule 3 during administration of adjuvant nivolumab (in which case the entire study will terminate). Therefore, a minimum of 6 patients and a maximum of 18 patients will be enrolled in the run-in phase.

DLT criteria are grade  $\geq 3$  immune-related adverse events, need to hold nivolumab for  $>28$  days due to toxicity, and for patients receiving concurrent nivolumab with chemoradiation, inability to complete chemoradiation or need to hold chemoradiation for  $>3$  days due to immune-related toxicity.

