## 3 Study Design

### 3.1 Characteristics

This is a Phase 2, single arm, open-label, multicenter study evaluating the feasibility of a treatment regimen comprised of nivolumab administered approximately every 2 weeks before and during chemoradiation and as an adjuvant therapy for 3 months to patients with stage II-IVB NPC who are planning to undergo chemoradiation treatment of their cancer.

A run-in phase will precede expansion, to establish basic feasibility of the nivolumab schedule. The run-in cohorts will include 6 patients at each dose schedule, with 2 planned changes in dose schedule if >33% toxicity or other DLT is observed. A minimum of 6 patients and maximum of 18 patients may be enrolled in the three run-in cohorts. The MTD schedule will be selected when 4/6 patients at a dose schedule complete therapy without grade 3-4 immune related toxicity. All patients will receive the same dose of nivolumab (240mg).

At the starting dose schedule, patients will receive nivolumab for 1 cycle prior to initiation of chemoradiation (approximately 14 days). Patients will subsequently continue with nivolumab every 14 days until completion of chemoradiation. In dose schedule 2, patients will start nivolumab concurrent with start of chemoradiation. In dose schedule 3, patients will start nivolumab after completion of chemoradiation (adjuvant nivolumab only).

DLT criteria are grade  $\geq 3$  immune-related adverse events, need to hold nivolumab for >28 days due to toxicity, and for patients receiving concurrent nivolumab with chemoradiation, inability to complete chemoradiation or need to hold chemoradiation for >3 days due to immune-related

toxicity.

The expansion phase will continue after the run-in phase has been used to establish the MTD schedule for nivolumab. The expansion phase will be powered to test the feasibility of completion of the program as compared to the current standard of care.

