### 3.3 Feasibility assessment in the run-in phase

A run-in phase will be conducted initially to determine feasibility. The main schema will be used as illustrated, but dosing of nivolumab will be subject to dose reduction if high grade immune related adverse events are observed.

Six patients will be enrolled for the initial run-in phase, starting with nivolumab dosing of 240 mg. Enrollment will cease until all 6 patients have completed concurrent chemoradiation and nivolumab. If 3/6 patients have experienced grade 3-4 immune related toxicity or other DLT during concurrent chemoradiation and nivolumab therapy, then the dose schedule will be changed to the next dose schedule and the run-in will restart at that schedule. In dose schedule 2, patients will start nivolumab concurrently with chemoradiation and there will be no priming dose prior to chemoradiation. Using these same procedures, there may be one further change to dose schedule 3. In dose schedule 3, patients will not have priming or concurrent nivolumab and will only start nivolumab in the adjuvant phase after chemoradiation is concluded. No dose reductions of nivolumab will be allowed. No dose escalation will be allowed.

The run-in will cease when 4/6 patients or more have completed their specified concurrent nivolumab therapy at the same nivolumab dose schedule without experiencing grade 3-4 toxicity or other DLT, or alternatively, if 3/6 patients have experienced grade 3-4 toxicity or other DLT during the adjuvant phase at dose schedule 3 (in which case the entire study will terminate). Therefore, a minimum of 6 patients and a maximum of 18 patients will be enrolled in the run-in phase.

DLT criteria are grade  $\geq 3$  immune-related adverse events, need to hold nivolumab for  $>28$  days due to toxicity, and for patients receiving concurrent nivolumab with chemoradiation, inability to complete chemoradiation or need to hold chemoradiation for  $>3$  days due to immune-related toxicity.

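### The run-in go rule is worded three ways and does not mirror the schedule-change rule, so some six-patient cohorts have no stated decision and others meet two conflicting rules

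*Combined protocol and SAP*

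**What the plan says.** The run-in treats six patients per schedule, over up to three nivolumab schedules. The go rule appears three times:

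- Section 3.1: "The MTD schedule will be selected when 4/6 patients at a dose schedule complete therapy without grade 3-4 immune related toxicity".
- Section 3.3: at least 4 of 6 patients "have completed their specified concurrent nivolumab therapy at the same nivolumab dose schedule without experiencing grade 3-4 toxicity or other DLT".
- Section 8.2.2: at least 4 patients "completed chemoradiation and nivolumab therapy at the same nivolumab dose schedule without experiencing grade 3-4 toxicity or other DLT".

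The change rule for schedules 1 and 2 is, in 8.2.2, "If 3 or more of the first 6 patients experience grade 3-4 immune related toxicity or other DLT during concurrent chemoradiation" and nivolumab. Section 3.3 has the same event but writes the threshold as 3/6. The abstract and 3.1 put it differently again: "with 2 planned changes in dose schedule if >33% toxicity or other DLT is observed".

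The study terminates at schedule 3, in 8.2.2, "if 3/6 patients have experienced grade 3-4 toxicity at dose schedule 3 during administration of adjuvant nivolumab"; in 3.3, "if 3/6 patients have experienced grade 3-4 toxicity or other DLT during the adjuvant phase at dose schedule 3". At that schedule "patients will not have priming or concurrent nivolumab and will only start nivolumab in the adjuvant phase".

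The DLT list is the same in the abstract, 3.1, 3.3 and 8.2.2. It covers immune-related events of grade 3 or higher and a nivolumab hold of more than 28 days for toxicity. For patients on concurrent nivolumab it adds inability to complete chemoradiation, or a chemoradiation hold of more than 3 days for immune-related toxicity. Section 8.2.5 makes any dosed patient evaluable and replaces only those who drop out before nivolumab.

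**The concern.** A cohort rule should give exactly one decision for every possible cohort. That requires go and change to be complements: the same event, the same window, and thresholds that meet. Here the go rules in 3.3 and 8.2.2 add a completion condition and leave out the immune-related qualifier that the change rule carries. The go rule in 3.1 has the qualifier but leaves out other DLTs. The 3.3 go rule asks for completed concurrent nivolumab, which schedule 3 does not have. The termination rule lacks the qualifier in both sections, and in 8.2.2 it also lacks other DLTs.

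The run-in picks the schedule that goes into the expansion, its patients at that schedule count in the primary endpoint (3.4 and 8.2.3), and it can end the study. Where the text gives no decision, or two, someone has to choose a reading with the cohort's data already in hand.

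**Working it through.** **The plan's own figure.** One schedule: 6 × 1 = 6. Three schedules: 6 × 3 = 18. The stated minimum of 6 and maximum of 18 reproduce. The plan gives no error rate for the run-in rule.

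**Threshold in the abstract and 3.1.** 2/6 = 33.3%, which literally exceeds 33%. Two affected patients would therefore trigger a change under that wording, while 4 clean patients of 6 is a go.

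**Cohorts that meet neither rule (8.2.2 read literally).** Class each of six patients as a success (s), a DLT (d) or neither (n), with s + d + n = 6.

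- Possible splits: C(8,2) = 28.
- Go needs s ≥ 4 and change needs d ≥ 3. Both together would need 7 patients, so they never coincide.
- Undecided means s ≤ 3 and d ≤ 2: 4 × 3 = 12 splits.

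| Patients in neither count | Undecided / possible splits |
|---|---|
| 0 | 0 / 7 |
| 1 | 1 / 6 (s = 3, d = 2) |
| 2 | 2 / 5 |
| 3 | 3 / 4 |
| 4 | 3 / 3 |
| 5 | 2 / 2 |
| 6 | 1 / 1 |
| Total | 12 / 28 |

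**Cohorts that meet both rules (3.1 go against 8.2.2 change).** Take two patients with immune-related grade 3-4 toxicity, one whose chemoradiation is held for more than 3 days for grade 2 immune-related toxicity and who then finishes, and three with no event. Four patients (1 + 3) satisfy the 3.1 go rule, and three (2 + 1) satisfy the 8.2.2 change rule.

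**What remains on the intended reading.** Suppose grade 3-4 toxicity means immune-related toxicity throughout. The neither group then shrinks to dosed patients who do not complete and have no DLT, for example after withdrawal. A patient who misses a concurrent dose during a grade 2 hold may also belong there, depending on how completion is read. The documents give no rate for this, so the rates below are assumptions. With p_D the DLT probability and p_N the probability of non-DLT non-completion per patient,

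P(no decision) = Σ over d = 0..2 and s = 0..3 of [6! / (d! s! n!)] · p_D^d · p_N^n · (1 − p_D − p_N)^s, with n = 6 − d − s.

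| p_D | p_N = 0.02 | p_N = 0.05 | p_N = 0.10 |
|---|---|---|---|
| 0.10 | 0.01 | 0.03 | 0.08 |
| 0.20 | 0.03 | 0.07 | 0.16 |

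**After the repair.** With six DLT-evaluable patients and one event, d = 0, 1 or 2 is go and d = 3, 4, 5 or 6 is change or terminate. All seven outcomes have exactly one decision.

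**The case against.** The strongest reply is that the intent is clear. Adding other DLTs after grade 3-4 toxicity implies that the toxicity named is itself a DLT, and the DLT list has only immune-related events at grade 3 or higher. Section 3.1 and both change rules carry the qualifier, and 3.3 opens by referring to high-grade immune-related events. This stands, and it rules out two inferences a reader might draw.

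- That grade 3 radiation mucositis, which 5.2.2 calls common, would block success and leave most cohorts undecided. Only an isolated literal reading of the 3.3 and 8.2.2 go rules gives that.
- That three non-immune grade 3-4 events at schedule 3 would end the study. Section 8.2.2 says it is nivolumab toxicity that is assessed there, in the adjuvant phase, and the rule is reached only after schedules 1 and 2 have both failed.

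It can also be said that 3.3 and 8.2.2 fix the window for schedules 1 and 2 as the concurrent phase, that failure to complete chemoradiation is already in the DLT list, and that Appendix 2 provides for a written report and authorization by the DSMC Chair. These points narrow the problem without closing it. The non-DLT non-completer still has no place, the 3.3 go rule still cannot be applied at schedule 3, and Appendix 2 supplies oversight but no rule.

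**Conclusion.** The point holds as a fault in the decision rules as written. Three go wordings, two termination wordings and a percentage threshold do not agree, and they can produce no decision or two opposite ones. On the probable intent the remaining gap is modest: about 0.01 to 0.16 over the assumed rates, and zero if every dosed patient either completes or has a DLT. The 12 of 28 splits describe the literal text and are not equally likely, so they should not be read as a 43% chance of an undecided run-in. The documents do not support a claim that the run-in would probably stall or that the study would be stopped for chemoradiation toxicity.

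**What to change.** Use one rule in the abstract, 3.1, 3.3 and 8.2.2:

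*Go if 2 or fewer of 6 DLT-evaluable patients have a DLT in the window; change to the next schedule, or terminate at schedule 3, if 3 or more do. The window is the priming and concurrent phase for schedules 1 and 2, and the adjuvant phase for schedule 3.*

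Then:

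1. Wherever the go and termination rules still name the event, write grade 3-4 immune-related toxicity or other DLT.
2. Replace the 33% threshold with 3 or more of 6.
3. State that a run-in patient who leaves the window without a DLT for a non-toxicity reason is replaced for the DLT decision.
4. Do not narrow the DLT list. Keep inability to complete chemoradiation because of toxicity as a DLT. If it were limited to immune-related causes while the separate completion condition is dropped, six patients who all failed to finish chemoradiation from other toxicity would count as 0 DLTs and a go.

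The cost is a wording amendment with no new procedures. Each replacement under item 3 adds one patient to the run-in, so 6 to 18 would refer to DLT-evaluable patients. A replaced patient has received nivolumab and so remains evaluable under 8.2.5.
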